12.3 Accrual Objectives

Phase I

A minimum of 12 patients will enroll in the Phase I trial, following a 3+3 design for 3 cohorts. We estimate that 10 patients will enroll at UCSF, and 7 patients each at Duke and Vanderbilt. Phase I completed at UCSF with 28 patients enrolled as 03/10/2015

Phase II

This study will enroll 56 patients (n=22 in the first stage and n=34 in the second stage) in the Phase II portion with the assumed 10% dropouts. We estimate that 26 patients will enroll at UCSF and 15 each at Vanderbilt and Duke.

12.4 Estimated Duration of Study

The Phase I study is expected to complete accrual within 1.25 years, and the Phase II study is expected to complete accrual over a time course of 2.5 years.

12.5 Data Safety Monitoring

See Section 16.0.

12.6 Replacement Policy

Phase I

For any dose cohort, if a patient is removed from study for reasons that are clearly not treatment-related, then an additional patient will be accrued to that dose level.

Phase II

Patients who have no evaluation measures after starting therapy, and stop therapy for reasons other than progression or toxicity will be replaced. Patients who receive only one dose of eribulin or less than 14 days of PLX3397 for reasons other than progression or toxicity will be replaced.

12.7 Pharmacokinetic studies

Pharmacokinetic studies will be performed as outlined in section 14.4. Serum concentrations of PLX3397 with eribulin will be assessed by ELISA at Plexxikon Inc. and will be used to calculate the values of PK parameters, including maximum serum drug concentration (C_{max}), area under the concentration-time curve from time zero to infinity (AUC 0-inf), systemic clearance (CL), volume of distribution (V), and elimination half-life (t_{1/2}). Descriptive statistics (including number, mean and/or median, standard deviation, and coefficient of variation) will be used to describe the concentration time data. Where appropriate, these data may be combined with data from other studies as part of a metaanalysis. The influence of exposure on clinical safety parameters (e.g., selected AEs) will be explored. Results of the PK analysis will be evaluated in conjunction with available safety and pharmacodynamic data.

12.7 Correlative studies

Due to the small sample sizes expected from the proposed study design, the correlative studies will be hypothesis generating, but will also help provide pilot data to inform eligibility and follow up of future trials using an MO- \square targeting strategy. CSF1 levels will be analyzed as a continuous variable and categorical variable based on median CSF change with treatment. Mean and 95% confidence intervals of CSF1 levels will be estimated and compared for differences between dose cohorts. As a continuous measure, ANOVA and Pearson correlation will compare CSF1 levels between PLX3389 dose cohorts and response groups. As a categorical measure, Chi-square tests will determine the associations between tumor subtype (molecular profile) and immune profile (dichotomous variable) and between tumor molecular profile and CSF1 groups. FACS analysis of leukocyte populations as a percent of total CD45+ cells will be evaluated among the outcome groups, PFS and ORR. The relationship between mean and median immune infiltrate and continuous quantitative measurements of tumor classification will be reported using either parametric (Pearson) and Fisher's exact tests or nonparametric (Spearman) correlation coefficients and Rank tests and 95% confidence intervals for each statistic.

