2.2.2 Phase II

- To determine the response rate of PLX3397 in combination with eribulin in patients with chemotherapy pre-treated triple negative metastatic breast cancer.
- To determine the duration of response from the above therapy in this patient population.
- To determine the safety and tolerability of PLX3397 in combination with eribulin in this patient population.
- Correlative studies:
 - Correlation of CSF1 levels and response/duration of response to treatment.
 - Correlation of immune profiling in blood with PLX3397 treatment.
 - Correlate tumor immune profile before and after therapy with tumor subtype and response to therapy.

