8.2.3 During Subsequent Cycles (Cycle 2 and beyond)

The following assessments will be performed prior to receiving treatment on Day 1:

- Medical history and physical examination
- Review of concomitant medications
- Laboratories, including complete blood count, chemistry panel and liver function tests. Urine Pregnancy test will only be done for women of childbearing potential (Cycle 3+)
- Blood for CSF1 and leukocyte phenotyping (Cycle 2 and 4 Day 1 only)
- Blood for pharmacokinetics (Cycle 2, Phase Ib only)

The following assessments will be performed after receiving treatment on Day 1:

- Blood for pharmacokinetics will be drawn at 2 hours post treatment (C2, Phase Ib only)

The following assessments will take place on Day 8:

- Laboratories, including complete blood count with differential
- Review of concomitant medications

The following assessment will take place on Day 15:

- Liver function tests (Cycles 2 and 3 only)

Scans including all measurable and/or evaluable disease will be obtained every 6 weeks and at End of Treatment. Patients with either CR or PR and who have received at least 6 cycles of therapy may reduce the frequency of scans to every 9 weeks.

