14.6.1 Evaluation of baseline biomarkers most likely to predict response to MØ-targeted therapy

We will establish baseline values and variability of immune, and CSF1 measures in pts enrolled in phase I and phase II trials, and correlate these measures to magnitude of change in serum CSF1 levels and clinical response. Pts will be categorized as “good” or “poor” responders based on median change in serum CSF1, clinical response based in RECIST v1.1 imaging criteria at 12 wks and TTP. We will determine whether the tumor phenotype (ER, PR, HER2, and ki67), immune signature (CD68lo/CD4lo/CD8hi vs. CD68hi/CD4hi/CD8lo) and CSF1 signature at initial diagnosis (obtained from archived tumor blocks) correlates with response. In addition, we propose to explore whether the baseline immune and CSF1 signature differ between the early stage setting (derived from ongoing studies) and pts with MBC enrolled on this trial.

14.6.2 Evaluation of dynamic tissue and blood biomarkers most likely to show early biologic changes that predict clinical response

Identify whether leukocyte subpopulations are altered with PLX3397 treatment alone in a cohort of pts with metastatic TNBC. The lead-in design of the trial will allow evaluation of systemic response to PLX3397 alone in the absence of systemic chemotherapy (CTX). We will determine whether this single-agent therapy modulates leukocyte complexity in blood, with serum CSF1 measured between day -7/-5 and day 0/1. In addition, if ongoing studies demonstrates that core biopsy or FNA can reliably recapitulate the immune signature obtained from surgical samples, repeat biopsies will be used to determine whether immune infiltrate in tissue is modulated with PLX3397 treatment. This will provide confirmation that PLX3397 results in the expected macrophage, DC and T cell modulation at the tissue level.

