14.6.3 Determine magnitude of change in serum CSF1

Determine whether magnitude of change in serum CSF1 is associated with: 1) dose levels of PLX3397 and 2) response to therapy. For patients on the phase I trial, CSF1 levels will be

drawn at Cycle 1, days 1 and 2, and Cycle 2, day 1. For patients on the phase II trial, CSF1 levels will be drawn at the start of the PLX3397 lead-in, at day 5 to 7 before the start of eribulin, at Cycle 1, day 1, and Cycle 2, day 1.. Baseline CSF1 and magnitude of change in CSF1 will be correlated to dose of PLX3397 and treatment response group.

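### The continuous CSF1 comparison across dose cohorts in 12.7 uses levels, the objectives speak of change, and neither adjusts for the pre-dose value

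*Combined protocol and SAP*

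**What the plan says.** Section 12.7 (Correlative studies) treats CSF1 in two ways. As a continuous measure: "As a continuous measure, ANOVA and Pearson correlation will compare CSF1 levels between PLX3389 dose cohorts and response groups". The sentence before that one also plans means and confidence intervals of levels by dose cohort. As a category, it is a "categorical variable based on median CSF change with treatment". No sampling visit is named for either.

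Elsewhere the emphasis is on change. The Phase Ib secondary objective in 2.2.1 is to relate the change in CSF1 during treatment to PLX3397 dose. Section 14.6.3 says "Baseline CSF1 and magnitude of change in CSF1 will be correlated to dose of PLX3397 and treatment response group".

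The pre-dose value is scheduled for everyone. In Phase Ib, 8.2.2 places the Cycle 1 Day 1 CSF1 draw before treatment. In Phase II, a footnote to Table 8-2 places the first draw before the first lead-in dose. Phase Ib on-treatment draws are at Cycle 1 Day 2 and Cycle 2 Day 1 (Table 8-1, 14.2).

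For outcome, 2.2.2 lists "Correlation of CSF1 levels and response/duration of response to treatment", 14.6.1 classifies patients partly by "clinical response based in RECIST v1.1 imaging criteria at 12 wks and TTP", and 12.7 adds "FACS analysis of leukocyte populations as a percent of total CD45+ cells will be evaluated among the outcome groups, PFS and ORR". Section 8.2.3 schedules "Blood for CSF1 and leukocyte phenotyping (Cycle 2 and 4 Day 1 only"), and Table 8-2 agrees for Phase II. Sections 14.2 and 14.6.3 end CSF1 sampling at Cycle 2 Day 1, and 14.3 ends Phase II leukocyte sampling at day 0/1.

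**The concern.** Read with 2.2.1 and 14.6.3, section 12.7 leaves open whether the dose comparison is of the on-treatment level or of the change from baseline. The choice matters in a small Phase Ib (28 patients over several dose levels). An analysis of levels puts all between-patient spread at baseline into the error term. An analysis of change removes the baseline but adds its noise, and does worse than levels when baseline and on-treatment values are only weakly correlated. The correlation is unknown in advance, so either choice can be the poor one. Adjusting for baseline avoids having to guess.

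A second, smaller matter is that 12.7 relates biomarkers to outcome without naming the sample, while the visit schedule contains a draw at about week 9 that section 14 does not mention.

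**Working it through.** The plan states no power, SD, effect size or baseline correlation for 12.7, so there is no figure to reproduce. What follows is a range under stated assumptions.

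**Residual variance.** Let the within-cohort variance be 1 at both visits and the baseline correlation be ρ.
- Level: v = 1
- Change: v = 2(1 − ρ)
- Baseline-adjusted: v = 1 − ρ² = (1 − ρ)(1 + ρ)

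Since 1 + ρ ≤ 2, adjustment never has more residual variance than change, and it never exceeds 1. Change beats levels only if ρ > 0.5.

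**Like-for-like linear dose trend.** Assumed: three cohorts of 8 (the documents give 28 enrolled but not the split), slope 0.5 SD per level, two-sided 5%. Doses of 600, 800 and 1000 mg are equally spaced, so a Pearson correlation with dose is the same test as a linear trend. With scores −1, 0, 1 the sum of squares is 8 + 0 + 8 = 16, and the noncentrality is λ = 0.5² × 16 / v = 4/v. Error degrees of freedom are 22, or 21 with the covariate. For the adjusted model λ is multiplied by 22/23, the average loss from chance correlation between dose and baseline.

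| ρ | Levels: λ, power | Change: λ, power | Adjusted: λ, power |
|---|---|---|---|
| 0.3 | 4.00, 0.48 | 4/1.4 = 2.86, 0.37 | 4/0.91 × 22/23 = 4.20, 0.50 |
| 0.5 | 4.00, 0.48 | 4/1.0 = 4.00, 0.48 | 4/0.75 × 22/23 = 5.10, 0.58 |
| 0.7 | 4.00, 0.48 | 4/0.6 = 6.67, 0.69 | 4/0.51 × 22/23 = 7.50, 0.74 |

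Simulation of the same setting gives about 0.48–0.50 for levels, 0.36, 0.48 and 0.71 for change, and 0.50, 0.57 and 0.76 for adjustment. Agreement is within about 0.02. At ρ = 0 adjustment costs about 0.02 (0.46 against 0.48).

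**Second check, unordered cohorts.** n = 28 split 9/9/10, Cohen f = 0.4 (both assumed), λ = 28 × 0.16 / v = 4.48/v, with 2 and 25 (or 24) degrees of freedom and no allowance for chance imbalance. Power is 0.41 on levels at any ρ. At ρ = 0.3, 0.5 and 0.7 it is 0.31, 0.41 and 0.63 on change, and 0.45, 0.53 and 0.70 with adjustment. The ordering is the same.

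**Week-9 sample (note only).** Assume constant hazard and the null rate of 39% progression-free at 90 days. Then S(42) = 0.39^(42/90) = 0.644 and S(84) = 0.39^(84/90) = 0.415. The share of 12-week failures already gone after the week-6 scan is (1 − 0.644)/(1 − 0.415) = 0.61. At the 57% alternative, S(42) = 0.769 and S(84) = 0.592, and the share is 0.231/0.408 = 0.57.

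**The case against.** The strongest reply is that the plan already uses baseline. Section 12.7 forms categories by median change, and 14.6.3 relates both baseline and change to dose and response. That is correct. A reader might infer from the sentence on levels that baseline is left out altogether, and the documents do not support that. What remains is the absence of a baseline-adjusted model and the unresolved choice between level and change.

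It can also be said that no power loss is demonstrated, since every input is assumed. That stands too. At ρ = 0.3 the gain over levels on a like-for-like trend is about 0.02. Comparing adjusted trend with unordered ANOVA would overstate it, because part of that difference comes from ordering the doses, which the planned Pearson correlation already does.

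A third reply is that conditioning on baseline would remove the question in 14.6.1 of whether baseline itself predicts response. That is a fair limit on the fix, which is therefore confined to the on-treatment dose comparison.

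A stronger inference is tempting: that week-9 biomarker results will be biased by guarantee time and need a landmark analysis. The documents do not support it. No passage assigns the Cycle 4 Day 1 value to an outcome analysis, and 14.6.2 centres on the lead-in change, which is complete when the PFS clock starts. Even if the week-9 value were used, all patients with it share nearly the same event-free period. Moving the origin would subtract a near-constant, leave the association essentially unchanged, and recover none of the missing failures. The real limit is the population to which such a result applies.

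**Conclusion.** The point holds as a free improvement. The dose-cohort comparison of continuous CSF1 is written for levels in 12.7 and for change in 2.2.1 and 14.6.3, and no model adjusts for a baseline value that is scheduled in every patient. Under the assumptions shown, adjustment raises power over levels by about 0.02, 0.10 and 0.26 at correlations of 0.3, 0.5 and 0.7. Over change scores the gain is about 0.13, 0.10 and 0.05. These sizes rest on an assumed cohort split, slope and correlation. The ordering of residual variances does not, apart from the cost of about 0.02 when the correlation is near zero.

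The dose comparison concerns Phase Ib, and the week-9 sample concerns Phase II. Section 12.7 says "the correlative studies will be hypothesis generating", and no trial decision depends on these analyses, so the consequence is limited to precision and clarity.

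**What to change.** In 12.7 (Correlative studies):
- For the on-treatment CSF1 comparison across dose cohorts, replace ANOVA/Pearson on levels with a linear model of log CSF1 at a named visit (Phase Ib: Cycle 1 Day 2 and Cycle 2 Day 1) on baseline log CSF1 and dose as an ordered term. Report the dose effect with its confidence interval.
- Keep the analysis of baseline CSF1 against response in 14.6.1 and 14.6.3 as a separate item.
- State which sample each biomarker-outcome analysis uses.
- Correct PLX3389 to PLX3397.

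Reconcile Table 8-2 and 8.2.3 with 14.2, 14.3 and 14.6.3 on the Cycle 4 Day 1 draw. If that sample is related to outcome, say that the result applies only to patients still progression-free at about week 9.

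The cost is wording, plus one degree of freedom in the model. No new samples or visits are needed.

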12.2 Analysis Plan

Primary Efficacy Endpoint

Demographics and Baseline Characteristics

Demographic data (age, sex, race, ethnicity, body weight) and baseline disease characteristics will be tabulated and summarized and presented in data listings.

Progression Free Survival

Progression-free survival at 3 months (PFS) is defined as the proportion of patients alive and progression-free 90 days after Study Day 1. Duration of PFS is defined as the time from Study Day 1 to the earlier of disease progression or death due to any cause.

Progression free survival will be calculated from the first administration of PLX3397 with eribulin. The analyses of PFS will be performed using the Per Protocol population. These analyses are designed to include only objective progression events per the RECIST v1.1 criteria. Patients who do not have any post-baseline tumor assessments will be right censored on the date of Study Day 1. Patients who receive subsequent anti-cancer therapy before experiencing an event will be right censored at the date of the last tumor assessment prior to the date of initiation of subsequent therapy. Patients who have not experienced an event (and are not otherwise censored) at the time of data cutoff will be right censored on the date of their last tumor assessment

PFS will be estimated as a simple proportion based upon the results of the 12-week tumor assessment. Patients for whom this assessment is not performed will be included as failures, even if known to be alive at this timepoint. Confidence intervals will be provided. PFS and duration of PFS will also be estimated using Kaplan-Meier methods with associated confidence intervals.

Secondary and Supportive Efficacy Endpoints

Objective Response Rate

The objective response rate (ORR) is defined as the proportion of patients for whom the best overall response at the time of data cutoff is confirmed CR or confirmed PR as assessed per RECIST v 1.1 criteria. A table defining the derivation of best overall response to be applied will be provided in the SAP.

The analysis of ORR will employ the Per Protocol population. Patients who do not have any post-baseline tumor assessments will be counted as non-responders.

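### The exploratory biomarker analyses use PFS and TTP only as outcome groups, and test CSF1 change against molecular profile only through a median split; both discard information the trial already collects

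*Combined protocol and SAP*

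**What the plan says.** Section 12.7 (Correlative studies) puts CSF1 on two scales: "CSF1 levels will be analyzed as a continuous variable and categorical variable based on median CSF change with treatment". The continuous version has named methods: "As a continuous measure, ANOVA and Pearson correlation will compare CSF1 levels between PLX3389 dose cohorts and response groups". The categorical version is used in a chi-square test of association "between tumor molecular profile and CSF1 groups". Leukocyte populations stay as percentages of CD45+ cells and "will be evaluated among the outcome groups, PFS and ORR"; neither a cut-point nor a test is given.

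Section 14.6.1 classes patients as good or poor responders from the median change in serum CSF1, "clinical response based in RECIST v1.1 imaging criteria at 12 wks and TTP". Section 14.6.3 relates baseline CSF1 and its change to dose and treatment response group.

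The time data exist. In section 12.2, "Duration of PFS is defined as the time from Study Day 1 to the earlier of disease progression or death due to any cause", and both PFS and TTP are estimated by Kaplan-Meier. Section 2.2.2 lists as a Phase II objective "Correlation of CSF1 levels and response/duration of response to treatment".

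**The concern.** Two measures are reduced to categories before they are compared.

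The first is time to progression. Once PFS or TTP becomes a group, early and late progressions on the same side of the cut count alike, and patients censored before the cut have no natural place. The Phase II objective on CSF1 and duration of response has no analysis that uses duration.

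The second is CSF1 change against tumor molecular profile. Only a median-split version is named. A sample median also belongs to this trial and does not carry over as a threshold elsewhere.

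Section 14.6 makes biomarkers that predict, or give early evidence of, response the main aim of the correlative work. Section 12.7 says the samples will be small and the results will inform eligibility and follow-up in later trials. Small samples are a reason to keep the information that has been collected.

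**Working it through.** **1. The planned comparisons side by side**

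| Comparison | Marker scale | Outcome scale | Method named |
|---|---|---|---|
| Leukocytes vs PFS, ORR (12.7) | percentage | groups | none |
| CSF1 vs response (12.7, 14.6.3) | continuous | groups | ANOVA, Pearson |
| CSF1 vs dose cohort (12.7, 14.6.3) | continuous | not applicable | ANOVA, Pearson |
| CSF1 change vs molecular profile (12.7) | median split | not applicable | chi-square only |
| Baseline markers vs response (14.6.1) | various | good/poor | correlation, unspecified |
| CSF1 vs duration of response (2.2.2) | not stated | duration | none |

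No row uses a time-to-event model.

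**2. Inputs**

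The plan states no effect size, sample size or power for these analyses, so there is no figure to reproduce. From the documents come 51 evaluable patients and progression-free rates of 39% and 57% (12.1), scans every 6 weeks, 2.5 years of accrual (12.4), 28 Phase Ib patients (12.3), and a median PFS of 2.23 months on eribulin in triple-negative disease (1.2).

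Under an exponential model these agree: 0.5^(3/2.23) = 0.394, and 57% at 3 months corresponds to a median of 3 × ln 2 / (−ln 0.57) = 3.70 months.

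Assumed here: a normal marker, a hazard ratio (HR) per SD of 1.4 to 1.7, 3 months of follow-up after accrual, 5% loss per month, 2-sided 5% tests, and a PFS cut at 12 weeks.

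**3. Grouping PFS: simulated power**

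Cox regression with Efron ties (size 0.044 to 0.052) is compared with a t-test of the marker by 12-week status. Cox values are rounded from repeated runs. For the t-test, the lower value at median 3.7 months counts unassessed patients as failures and the higher value excludes them.

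| Median PFS | HR per SD | Cox | 12-week t-test | Loss (points) |
|---|---|---|---|---|
| 3.7 months | 1.4 | 0.47 | 0.23 to 0.28 | 19 to 24 |
| 3.7 months | 1.5 | 0.60 | 0.32 to 0.37 | 23 to 28 |
| 3.7 months | 1.7 | 0.81 | 0.51 to 0.59 | 22 to 30 |
| 2.23 months | 1.4 | 0.46 | 0.31 to 0.33 | 13 to 15 |
| 2.23 months | 1.5 | 0.65 | 0.45 to 0.47 | 18 to 20 |
| 2.23 months | 1.7 | 0.84 | 0.62 to 0.69 | 15 to 22 |

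**4. Sensitivity to follow-up** (n=51, HR 1.5, 12-week rate 48%)

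| Maximum follow-up | Cox | t-test | Loss (points) |
|---|---|---|---|
| 18 weeks | 0.517 | 0.496 | 2 |
| 26 weeks | 0.564 | 0.486 | 8 |
| 52 weeks | 0.651 | 0.509 | 14 |
| 104 weeks | 0.698 | 0.497 | 20 |

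The gain comes almost entirely from events after week 12.

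**5. Median split of CSF1 change**

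Hand check for groups of 25 and 26 with a standardised difference d = 0.8:

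- Continuous: 0.8 × √(25 × 26 / 51) = 2.86, so power ≈ Φ(2.86 − 1.96) = Φ(0.90) ≈ 0.82.
- Median split: the shares above the pooled median are about Φ(0.4) = 0.655 and 0.345, a difference of 0.31. The null standard error is 0.5 × √(1/25 + 1/26) = 0.14, so power ≈ Φ(0.31/0.14 − 1.96) = Φ(0.25) ≈ 0.60.

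Simulation for d = 0.6, 0.8, 1.0 gives 0.56, 0.81, 0.93 (t-test) against 0.34, 0.58, 0.76 (chi-square, no continuity correction): losses of 22, 23 and 17 points. Another run at d = 0.8 gave 25 points. With a 38/13 split the loss is 16 to 21 points. In Phase Ib at 14/14 it is about 7 points at d = 0.6, 12 at d = 0.8 (0.535 vs 0.419) and 15 at d = 1.0 (0.722 vs 0.569).

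**The case against.** The strongest reply is that section 12.7 calls these analyses hypothesis generating because samples are small, claims no power, and ties no trial decision to them. That stands. It limits the point to efficiency but does not favour grouping.

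Several stronger readings are tempting and are not supported:

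- **CSF1 is dichotomised throughout.** It is not. Continuous analyses are planned for dose cohorts and response groups. Only the molecular-profile comparison lacks one, and that is an association with a tumor feature, not a test of predicting response.
- **Outcome and marker are cut in the same test.** That would be costly: with 52 weeks of follow-up and HR 1.5, power falls from 0.651 (Cox) to 0.346 (2×2 chi-square). No test in 12.7 is specified that way: leukocytes stay as percentages, and the CSF1 groups are not tested against outcome.
- **The plan fixes a 12-week cut for leukocytes.** It names no cut. Twelve weeks is inferred from 14.6.1 and the primary endpoint.
- **Real predictors will probably be missed because of the grouping.** The documents give no effect sizes to support this, and Cox itself misses about 35 to 54% of effects at HR 1.4 to 1.5 in the table above.

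Two further limits stand. Event times are not complete for everyone: 12.2 uses the Per Protocol population and censors patients without a post-baseline scan at Day 1, and the Phase II calendar takes patients off study within 30 days of the last dose. Also, Phase II enrols only triple-negative disease, so an even molecular split there is an assumption.

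**Conclusion.** The point holds as an efficiency improvement to exploratory analyses. Biomarkers meet PFS and TTP only as groups, the duration-of-response objective has no matching method, and one CSF1 comparison exists only as a median split. These facts need no power assumption.

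The size does. For PFS it is roughly 13 to 30 points at n=51 under the assumed effects, accrual, loss rate and 12-week cut, shrinking to a few points if follow-up stops soon after week 12. For CSF1 change against molecular profile it is about 16 to 23 points at n=51 (25/26 or 38/13) and 7 to 15 in Phase Ib (14/14), for d of 0.6 to 1.0. No stated figure is wrong, and the primary analysis is unaffected.

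**What to change.** In sections 12.7 and 14.6.1:

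- Relate each baseline marker, and each lead-in change (before PLX3397 to Cycle 1 Day 1), to PFS and TTP by Cox regression with the marker on its continuous scale, log-transformed if skewed. Lead-in change is known when the PFS clock starts, at the first PLX3397 dose given with eribulin. A change measured later, such as at Cycle 2 Day 1, would need a landmark at that visit.
- Specify Efron or discrete-time handling of ties, because 6-week scans produce many tied event times.
- Keep the 12-week and ORR groups as descriptive summaries, and define them.
- State how the duration-of-response objective in 2.2.2 will be addressed.
- Compare continuous CSF1 change across molecular profiles by ANOVA, or Kruskal-Wallis if skewed, and use the median split for display only.

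The cost is a few sentences and a few lines of code, with no new data, patients or visits. The downside is reliance on proportional hazards and a log-linear marker effect, both of which can be checked with the same data. The wording should be settled before database lock.
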